The investigator must consult the medical monitor if subjects have not obtained a CR after Cycle 1 and prior to Cycle 2, and if there is any consideration to omit Cycle 2 of induction chemotherapy.

Subjects with cytogenetic and molecular mutations at screening must have cytogenetic and molecular mutation testing repeated at subsequent bone marrow examinations (Cycle 0 Day 14, Cycle 1 Day 14, count recovery, End of Study).

Subjects will undergo a daily CBC from Cycle 1 Day 14 (ie, count nadir) until count recovery at which time a bone marrow aspirate and biopsy will be performed.

Once a CR/CRi is confirmed on a recovery bone marrow examination (ie, the subject achieves < 5% blasts by morphology and flow cytometry), the subject will proceed to either allogeneic stem cell transplantation (SCT) or post-remission chemotherapy with cytarabine.

If CR/CRi is not achieved by the end of Cycle 2, the subject will be considered a treatment failure and will have met study efficacy endpoint criteria, but will remain on study for required study-related follow-up procedures.

Entospletinib + cytarabine post-remission (at least 3 cycles, and up to 4 cycles):

Post-remission chemotherapy will be offered to eligible subjects who have achieved CR/CRi and do not require or cannot proceed to allogeneic SCT. In addition, subjects who are awaiting a donor or transitioning to allogeneic SCT will be allowed to receive post-remission chemotherapy per investigator discretion. Therapy will consist of 3g/m² high dose cytarabine administered IV every 12 hours on Days 1, 3, and 5 (< 60 years of age) or 1g/m² cytarabine administered once daily on Days 1-5 (≥ 60 years of age) in combination with 400 mg ENTO every 12 hours on Days 1-28 of each 28-day cycle.

[figure not shown]
Subjects in whom definitive post-remission chemotherapy is planned will receive at least 3 and up to 4 cycles of cytarabine. Subjects who are awaiting a donor or transitioning to SCT may receive at least 1 and up to 4 cycles of cytarabine.

A bone marrow aspirate sample will be collected for disease assessment and biomarker research at the end of every 2 cycles (Cycle 2 Day 28 and Cycle 4 Day 28) and at suspected disease progression. Subjects who continue to maintain a CR/CRi after 3-4 cycles of post-remission chemotherapy will be offered maintenance with ENTO 400 mg every 12 hours for up to 12 cycles.

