Dose Modifications for Hematologic Toxicity for Entospletinib and Daunorubicin and Cytarabine and High Dose Cytarabine Maintenance

No dose modifications are planned for hematological toxicity for cytarabine and daunorubicin during induction chemotherapy. In subjects who require Cycle 2 induction, an ECHO/MUGA is recommended prior to starting Cycle 2 and daunorubicin will be administered if EF is $\geq 45\%$ per investigator discretion.

No renal dose reductions are necessary when standard dose cytarabine is used (100-200mg/m²/24hrs). Reduced doses should be considered when using high dose cytarabine as indicated below:

Glomerular Filtration Rate (mL/min)	Dose Administered
> 60	100%
46-60	60%
31-45	50%
< 30	Contraindicated

For cerebellar neurotoxicity \geq Grade 2 due to high dose cytarabine, discontinue high dose cytarabine for the remainder of the induction cycle.

If prolonged hematologic clinically significant Grade 3 or greater toxicity felt to be related to ENTO occur after Cycle 1, hold ENTO until it resolves to less than Grade 2. Then, restart ENTO with one dose level reduction.

Group B:

Cycle 0 will be defined as Days 1-14. Cycles 1-4 and maintenance therapy will be defined as Days 1-28. Subsequent cycles of therapy are to begin as soon as possible after Day 28. Delays of up to 14 days will not constitute a protocol violation.

Delays of longer than 14 days must be discussed with the PI and Medical Monitor; repeat BM aspiration and biopsy is required if treatment is delayed more than 4 weeks. Delays longer than 14 days are only permitted (but not required) under special circumstances after discussion with PI and Medical Monitor and permissible reasons for these extended delays include:

- Drug related myelosuppression (defined here as ANC $<$ 500/ μ L or platelet count $<$ 25,000/ μ L, with no evidence of AML in blood or marrow – including flow cytometry or cytogenetics). A repeat BM aspiration and biopsy is required if treatment is delayed more than 4 weeks.
- Ongoing febrile neutropenia or active infection in subjects with no evidence of AML. Note - this does not apply to subjects with febrile neutropenia/infection in the setting of active AML.
- Serious hemorrhagic complication in a subject who is refractory to platelet transfusions.

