ENTO 400 mg will be administered daily every 12 hours in combination with IV daunorubicin (Days 1-3) and cytarabine (Days 1-7) for up to 2 induction cycles (Cycle 1 and 2). Subjects must be able to receive 2 cycles of induction chemotherapy. Subjects with residual disease detected at the Cycle 1 Day 14 bone marrow evaluation proceed with Cycle 2 of induction chemotherapy. The start of Cycle 2 will depend on the timing and result of the disease assessment. Subjects are to continue receiving ENTO while awaiting disease assessment results.

The investigator must consult the medical monitor if subjects have not obtained a CR after Cycle 1 and prior to Cycle 2, and if there is any consideration to omit Cycle 2 of induction chemotherapy.

If CR/CRi is achieved at the end of Cycle 1 or 2, the subject may proceed to SCT or will receive post-remission chemotherapy. If CR/CRi is not achieved by the end of Cycle 2, the subject is considered a treatment failure and will have met study efficacy endpoint criteria, but will remain on study for required study-related follow-up procedures.

Post-remission chemotherapy will consist of $3\text{g}/\text{m}^2$ cytarabine every 12 hours on Days 1, 3, and 5 (< 60 years of age) or $1\text{g}/\text{m}^2$ high dose cytarabine once daily on Days 1-5 (\geq 60 years of age) in combination with ENTO every 12 hours on Days 1-28 of each 28-day cycle for at least 3 cycles and up to 4 cycles. Subjects who are awaiting a donor or transitioning to allogeneic SCT may receive at least 1 cycle and up to 4 cycles of cytarabine.

Maintenance therapy will consist of ENTO 400 mg as a single agent every 12 hours on Days 1-28 of each 28-day cycle and will continue for up to 12 cycles as long as the subject is experiencing benefit or until the subject becomes a candidate for SCT. Extension of maintenance may occur on an individual basis if approved by the Principal Investigator.

If a subject discontinues study treatment (eg, as a result of an AE), every attempt should be made to keep the subject in the study to perform the required study-related follow-up and procedures. If this is not possible or acceptable to the subject or investigator, the subject may be withdrawn from the study.

For subjects enrolled to Group B Phase 1b/2 (Dose Escalation and Expansion):

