 - Subjects with cytogenetic and molecular mutations at screening must have cytogenetic and molecular mutation testing repeated at subsequent bone marrow examinations (Cycle 0 Day 14, Cycle 1 Day 14, count recovery, End of Study).

If CR/CRi is not achieved by the end of Cycle 2, the subject will be considered a treatment failure and will have met study efficacy endpoint criteria, but will remain on study for required study-related follow-up procedures.

Phase 2 only: The following procedures will be conducted during each 28-day Post-Remission cycle on Days 1 and 28 (unless otherwise specified) for 3-4 cycles.

- ENTO will be administered orally every 12 hours for 28 days in combination with 3g/m² high dose cytarabine administered every 12 hours on Days 1, 3, and 5 (<60 years of age) or 1g/m² cytarabine administered once daily on Days 1-5 (≥60 years of age)
- Review prior/concomitant medication
- Record any adverse events
- Vital signs; including blood pressure, respiratory rate, pulse, temperature, oxygen saturation level (Day 1 of Cycle 2 and Cycle 4)
- Complete physical examination (Day 1 of Cycle 2 and Cycle 4)
- Obtain smoking status for past 28 days (Day 1 of each cycle)
- ECOG performance status (Day 28 of Cycle 2 and Cycle 4)
- Urine pregnancy test (for all female subjects unless surgically sterile or menopausal prior to dose on Day 1)
- Obtain blood samples for:
 - Chemistry (Day 28 of Cycle 2 and Cycle 4)
 - Hematology (Day 28 of Cycle 2 and Cycle 4)
 - Coagulation (Day 28 of Cycle 2 and Cycle 4)
 - PK at pre-dose and 2 hours post-dose of ENTO (Day 5 and Day 28 of each cycle)
- Obtain bone marrow aspirate samples for disease assessment and biomarker testing on Cycle 2 Day 28 and Cycle 4 Day 28 or as clinically indicated. Biopsy will be used in the event the aspirate cannot be collected or analyzed (eg, dry-tap, hemodiluted specimen, or lack of spicules).

Phase 2 only: The following procedures will be conducted during each 28-day Maintenance cycle on Days 1 and 28 (unless otherwise specified).

- ENTO will be administered orally every 12 hours for 28 days and may continue up to 12 cycles as long as the subject is experiencing benefit or becomes a candidate for SCT. Extension of maintenance may occur on an individual basis if approved by the Principal Investigator.

- Review prior/concomitant medication
- Record any adverse events

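### The renal dosing table is tied to high dose cytarabine, a term the protocol never defines and gives to opposite post-remission regimens in different sections

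*Protocol*

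**What the plan says.** The renal rule for cytarabine is in Protocol Section 3.3, under the Group A heading on hematologic toxicity. It has two parts:

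- An exemption: "No renal dose reductions are necessary when standard dose cytarabine is used", with standard dose given as 100-200 mg/m² per 24 hours.
- A table, introduced by "Reduced doses should be considered when using high dose cytarabine as indicated below". Its rows are GFR above 60 (100% of dose), 46-60 (60%), 31-45 (50%) and below 30 (contraindicated).

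Section 3.3 attaches no dose in g/m² and no age group to *high dose*.

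The two post-remission regimens are described elsewhere. Section 3.1.2 calls the 3 g/m² regimen for subjects under 60 "high dose cytarabine administered IV every 12 hours on Days 1, 3, and 5", and describes the 1 g/m² regimen for subjects aged 60 or over as "cytarabine administered once daily on Days 1-5", without the label. Section 6.3.1 and footnote i of the Group A Phase 2 table in Appendix 2 use the labels in the same way. Section 3.4 reverses them: the 3 g/m² regimen is plain cytarabine and the 1 g/m² regimen is "high dose cytarabine once daily on Days 1-5".

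**The concern.** The label decides whether the table applies. Two sections of the same protocol, each followed literally, put different age groups inside a table that runs from full dose to contraindicated. A site that works from Section 3.4 and a site that works from Section 3.1.2 could reach different conclusions about the same subject, and nothing in Section 3.3 tells them which is meant.

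This is a safety dosing rule, so a contradiction weighs more than a missing detail would. It also bears on how post-remission exposure is read afterwards. SAP Section 4.2.3 summarizes chemotherapy by the number of doses received, so a reduced and a full administration count the same in that summary. Only the by-subject administration listings could show the difference.

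**Working it through.** No sample size, power or error rate is involved. The check compares every place that names a post-remission cytarabine regimen, with simple arithmetic for daily dose.

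**Labels side by side**

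| Protocol location | 3 g/m² every 12 h, Days 1, 3, 5 (<60 y) | 1 g/m² once daily, Days 1-5 (≥60 y) |
|---|---|---|
| 3.1.2 | high dose | no label |
| 6.3.1 | high dose | no label |
| Appendix 2, Group A Phase 2, footnote i | high dose | no label |
| 3.4 | no label | high dose |

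The doses, days and age split agree in all four places. Only the label moves: three places against one.

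**Daily dose against the exempt range (100-200 mg/m² per 24 h)**

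- 1 g/m² once daily = 1,000 mg/m² per day; 1,000/200 = 5 and 1,000/100 = 10, so 5 to 10 times the exempt range.
- 3 g/m² every 12 h = 2 × 3 = 6 g/m² per dosing day; 6,000/200 = 30 and 6,000/100 = 60, so 30 to 60 times the exempt range.

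Neither regimen is exempt, so each depends on the label to be inside the table.

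**Consequence of each literal reading**

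| Labels taken from | 3 g/m² (<60 y) | 1 g/m² (≥60 y) |
|---|---|---|
| 3.1.2, 6.3.1, Appendix 2 | in the table | neither exempt nor in the table |
| 3.4 | neither exempt nor in the table | in the table |

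**Does the surrounding text settle it?**

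- The heading above the table refers to high dose cytarabine maintenance. Group A has no such phase: maintenance is ENTO alone (Sections 3.1.2 and 3.4), and cytarabine belongs to the separately named post-remission phase.
- The next rule in Section 3.3, on cerebellar neurotoxicity, uses the same undefined term and speaks of the remainder of the induction cycle. Induction cytarabine is 100 mg/m² in Table 3-1 (Phase 1b), and the synopsis describes Phase 2 as similar. Section 3.3 is therefore not aligned with the treatment schedule, and intent cannot safely be read from it.

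**Table bands.** With whole-number GFR values, 31-45 is followed by below 30, so a GFR of 30 falls in no row.

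**Can affected subjects exist?** Group A has no upper age limit (Section 4.2). Renal eligibility is serum creatinine below 1.5 × ULN, waived if leukemia related (Table 4-1 and Section 4.2, criterion 5), with no GFR threshold. Entry criteria therefore do not exclude a GFR of 60 or below. The documents give no count.

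**The case against.** The strongest reply is that this is one misplaced adjective. The regimens themselves agree everywhere, Section 3.4 is the only outlier, and its literal consequence (1 g/m² in the table, 3 g/m² out) looks unintended. Section 3.3 contrasts standard dose with high dose, 1 g/m² daily is far above standard, and the heading makes no age split, so the table may be meant for both groups. That reading is reasonable, but it is inference: no section states it, and three places withhold the label from the 1 g/m² regimen. The documents do not settle the table's scope.

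Other parts of the reply stand and limit the point:

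- A reader might infer that subjects aged 60 or over have no renal guidance at all on one reading. They do have some. Section 5.1.1 sends sites to the package insert and institutional guidelines, and Section 1.10.2 permits adjustments in line with product information. Neither says which regimens the protocol's own table covers.
- A reader might set 100% of dose on one reading against 60%, 50% or contraindicated on the other. The protocol nowhere prescribes 100% for the 1 g/m² regimen at reduced GFR; where a regimen is not covered, the table is simply silent. Where it is covered, the lead-in asks only that reductions be considered.
- A reader might infer that exposure did differ between sites. Nothing in the documents shows this.

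**Conclusion.** The inconsistency is real. The scope of an advisory renal table rests on an undefined term that the protocol applies to opposite regimens, and no other section resolves it. It is an internal inconsistency in a safety dosing rule, not a design choice. The gap at GFR 30 is a smaller, separate drafting slip in the same table.

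Its reach is limited. Section 3.1.2 records Group A Phase 2 enrollment as complete, and the SAP introduction says the study will end early. In practice it concerns Group A Phase 2 subjects still due post-remission cytarabine, whose number is not given, and the interpretation of doses already given. The primary response endpoint is not affected, because SAP Section 6.1.2 closes the window for response at induction completion before Cycle 1 Day 1 of post-remission therapy. Event-free and overall survival extend past that point, but no effect on them is shown. The conclusion rests on reading the labels literally; whether the sponsor intended something else cannot be determined from the documents.

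**What to change.** Reconcile Protocol Sections 3.1.2, 3.3, 3.4 and 6.3.1 and Appendix 2 footnote i. Replace *high dose cytarabine* in Section 3.3 with the two regimens named by dose and age group, state for each whether the GFR table applies, and give GFR 30 an explicit row. Check the cerebellar neurotoxicity rule at the same time, since it uses the same term. Which regimen the table covers, and what the row at 30 says, are decisions for the clinical team.

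The cost is a wording change or a clarification letter to sites. If no subject is still due post-remission cytarabine, the sponsor can instead review the by-subject chemotherapy administration listings and note the ambiguity in the clinical study report. No analysis needs to change.

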For subjects entering the maintenance phase of treatment, drug related myelosuppression is a greater concern. However, it should again be noted that subjects with continued evidence of AML such as by flow or cytogenetics (even if morphologic blasts are $<$ 5%) should proceed with therapy in a timely way as described above.

For subjects with no evidence of AML, the first cycle of maintenance should proceed on Day 29 as long as marrow cellularity is \geq 10%. However, the second (or subsequent) cycles of maintenance therapy may be held until ANC is greater than or equal to 1000. If there is no evidence of ANC recovery after 14 days, repeat marrow evaluation is needed. If negative for disease and cellularity is \geq 10%, proceed with decitabine and ENTO at decreased doses. Bone marrow evaluation may be done sooner than 14 days at the discretion of the treating physician.

Dose Modifications for Non-Hematologic Toxicity for Entospletinib, Decitabine or Azacitidine

If the subject experiences any non-hematologic clinically significant Grade 3 or greater toxicity felt to be related to either agent during the induction phase beyond DLT assessment, hold the protocol therapy until it resolves to less than Grade 2. Then, if related to ENTO, restart ENTO

with one dose level reduction. If related to decitabine or azacitidine, the respective package insert should be followed for any dose reductions. If institutional guidelines are to be followed, contact the study team for additional guidance. If the toxicity recurs, subject will be removed from study. If protocol therapy is withheld for more than 2 weeks for toxicity related to protocol-based therapy or up to 4 weeks for any other reason, subjects will be removed from protocol. If a subject experiences pneumonitis at Grade 4, study treatment must be discontinued. For additional safety information, reference the package insert for decitabine and azacitidine.

Subjects who have been dose-reduced cannot be returned to a higher dose level.

Toxicities in an individual subject must resolve to less than Grade 2 or to baseline levels before proceeding with the next cycle of treatment.

Dose Modifications for Hematologic Toxicity for Entospletinib, Decitabine or Azacitidine

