In the event of Grade 4 neutropenia (ANC < 500/μL) that occurs with the second or subsequent cycles of maintenance and persists for 14 days or more or is associated with febrile neutropenia, further cycles of ENTO/decitabine shall be administered once ANC recovers to ≥ 1000/μL with a decrease in the number of days of decitabine and the dose of ENTO will be decreased by 1 dose level (ie, for the first occurrence omit the final day 5 dose of decitabine; for the second occurrence omit the final day 4 dose of decitabine). If there is no evidence of ANC recovery after 14 days, repeat marrow evaluation should be considered. Subjects who require a dose reduction below dose level -1 will not receive ENTO and instead will continue maintenance treatment with decitabine alone. If Grade 4 neutropenia that persists for 14 days or more (or grade 4 neutropenia associated with fever) recurs for the third time, discontinue the ENTO/decitabine. Similarly, in the event of neutropenia that occurs with the second or subsequent cycles of maintenance with azacitidine, and persists for 14 days or more or is associated with febrile neutropenia, the dose of azacitidine will be reduced according to [Table 3-8](#).

Thrombocytopenia

In the event of Grade 4 thrombocytopenia (platelets < 25,000/μL) that occurs with the second or subsequent cycles of maintenance and persists for more than 14 days (or >25,000/μL but requiring prophylactic platelet transfusions to maintain this over the 14 day period), further cycles of ENTO/decitabine shall be administered with a decrease in the number of days of decitabine and the dose of ENTO will be decreased by 1 dose level (ie, for the first occurrence omit the final day 5 dose of decitabine; for the second occurrence omit the final day 4 dose of decitabine). Subjects who require a dose reduction below dose level -1 will not receive ENTO and instead will continue maintenance with decitabine alone. If Grade 4 thrombocytopenia persisting for more than 14 days (or subject requires prophylactic platelet transfusions to maintain >25,000/μL over the 14 day period) recurs for the third time, discontinue the ENTO/decitabine. Similarly, in the event of thrombocytopenia that occurs with the second or subsequent cycles of maintenance with azacitidine, and persists for 14 days or more or is associated with prophylactic platelet transfusions, the dose of azacitidine will be reduced according to [Table 3-8](#).

Table 3-8. Azacitidine Dose Reductions

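### Protocol 3.3 (Group B) gives rules that cannot both be followed: dose or wait in prolonged neutropenia on decitabine maintenance, and delay or remove after a hold of more than 14 days

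*Protocol*

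**What the plan says.** All the rules are in the Group B part of Protocol 3.3.

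- **Delay text (general).** Cycles may slip by up to 14 days. Beyond that, "Delays longer than 14 days are only permitted (but not required) under special circumstances after discussion with PI and Medical Monitor". The listed reasons are drug-related myelosuppression without AML, "Ongoing febrile neutropenia or active infection in subjects with no evidence of AML", and serious hemorrhage in a platelet-refractory subject. A "repeat BM aspiration and biopsy is required if treatment is delayed more than 4 weeks", so delays of that length are foreseen.
- **Delay text (maintenance, no evidence of AML).** For the first cycle, "the first cycle of maintenance should proceed on Day 29 as long as marrow cellularity is" at least 10%; no ANC condition is set. Later cycles may be held for an ANC of 1000. If ANC has not recovered after 14 days, a repeat marrow is mandatory. If it is negative and cellularity is at least 10%, the instruction is to "proceed with decitabine and ENTO at decreased doses".
- **Non-hematologic toxicity.** The paragraph opens with toxicity in the induction phase. It later sets a rule for taking subjects off protocol after a hold: "withheld for more than 2 weeks for toxicity related to protocol-based therapy or up to 4 weeks for any other reason, subjects will be removed".
- **Neutropenia (maintenance, blasts below 5%).** After Grade 4 neutropenia (ANC below 500/µL) in the second or a later cycle that lasts 14 days or more or is febrile, "further cycles of ENTO/decitabine shall be administered once ANC recovers to" at least 1000/µL, with reductions. If ANC has not recovered after 14 days, a repeat marrow is only to be considered. For azacitidine the text gives a dose reduction and no ANC threshold for restarting.
- **Non-hematologic toxicity in CR/CRi maintenance.** A separate rule with its own hold and restart terms and no 2-week limit.

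**The concern.** A site with one subject in front of it should find one instruction. Here two paragraphs apply to the same neutropenic subject in remission; one directs dosing and the other directs waiting. For a hold caused by infection or hemorrhage, one paragraph lets the subject stay on protocol and another takes the subject off.

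The first conflict is a safety matter, because it decides whether decitabine and ENTO are given at a low ANC. Both conflicts also reach the analysis. SAP 4.3 tabulates important deviations, with a category (NW) for subjects who met a withdrawal criterion but were not withdrawn. If the criterion is ambiguous, the same conduct can be coded as compliant or as an important deviation, and exposure and discontinuation summaries will vary with the site's reading.

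**Working it through.** No power, alpha or sample-size figure depends on this point, so the check sets the rules side by side for two defined subjects.

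**Case 1: dose or wait.** Decitabine arm, no evidence of AML, second or later maintenance cycle, ANC below 500/µL for 14 days or more, repeat marrow negative, cellularity at least 10%.

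| Question | Delay text (maintenance) | Neutropenia text |
|---|---|---|
| Does it apply? | Yes: later maintenance cycle, no ANC recovery after 14 days | Yes: Grade 4 neutropenia of 14 days or more, second or later maintenance cycle |
| Repeat marrow | Mandatory | To be considered |
| Next cycle | Proceed now, at reduced doses | Once ANC is at least 1000/µL |
| Branch for dosing without recovery | Yes | None |

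An ANC below 500/µL is also below 1000/µL, so this subject meets both triggers. Proceeding without recovery and waiting for recovery cannot both be done. The general delay text adds a third possibility, a longer delay, but only as a permission subject to discussion.

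The conflict is written for decitabine. For azacitidine the maintenance delay text names only decitabine and ENTO, and the Neutropenia text sets no restart threshold. That is a gap, not a contradiction.

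**Case 2: delay or remove.** No evidence of AML, therapy held for a treatment-related active infection or serious hemorrhage.

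1. Two weeks is 2 × 7 = 14 days, so from day 15 the first limb of the removal sentence applies.
2. From day 15 the delay text permits the hold to continue, after discussion with the PI and Medical Monitor.
3. Four weeks is 4 × 7 = 28 days. The delay text foresees a hold beyond day 28 and requires a repeat marrow there; the subject is still on protocol.
4. Permitted delay and removal therefore collide from day 15 onward.

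**The last limb.** As written, a hold of up to 4 weeks for any other reason leads to removal. Read literally, a hold of a few days qualifies. Even if it is read as removal after more than 4 weeks, it still collides with step 3.

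**Meaning of removal.** The same paragraph speaks of removal from study when toxicity recurs and removal from protocol after a long hold. Neither phrase is tied to stopping treatment or to ending follow-up.

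**The case against.** **Scope of the removal sentence.** It stands under the non-hematologic heading, in a paragraph that opens with induction, and CR/CRi maintenance has its own non-hematologic rule without a 2-week limit. This stands. A reader might infer that a responder with prolonged neutropenia faces removal at day 15 of any treatment-related delay. The documents do not support that: the sentence reaches pure neutropenia only through its unrestricted wording.

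**Permission, not order.** The extended delay is gated by cause and by discussion, and its listed causes could be read as exceptions to the removal limit. The first half stands, so it would be wrong to describe four competing orders. The exception reading is possible, but neither text states it.

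**Specific over general.** The Neutropenia text covers Grade 4 counts and the delay text any failure to reach 1000, so the narrower might govern. Alternatively, the delay text might supply the missing no-recovery branch. These two readings give opposite answers for Case 1 and the protocol does not choose between them. The Neutropenia text has its own sentence on non-recovery, which does not refer back or allow dosing.

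**Consequences.** A reader might infer that removal ends EFS and OS follow-up. Protocol 6.4 asks sites to make every attempt to keep subjects in the study, 6.4.1 continues survival follow-up after a subject withdraws from treatment, and 6.5 follows survival for up to 3 years, so that loss is not established. A reader might also infer that the event is common because the protocol provides reductions for count toxicity after Cycle 3. That rule is conditional, follows text on active AML and gives no rate.

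**Practical value.** SAP Section 1 records that Group B Phase 2 recruitment closed permanently and that the study will end early. This lowers the number of future subjects affected; it does not settle the rule for subjects on maintenance or for deviation coding.

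**Conclusion.** The point holds in two parts. The dose-or-wait contradiction for decitabine maintenance is firm: both paragraphs apply by their own terms, and no heading or other section resolves it. The delay-or-remove contradiction is clear for treatment-related infection or hemorrhage, most of all in induction, and the last limb of the removal sentence is defective on its face.

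The size cannot be given as a rate. The decitabine subjects planned were up to 14 in Phase 1b plus 40 / 2 = 20 randomized, that is 34 at most under the plan. The documents do not say how many reached a second maintenance cycle, and recruitment stopped short.

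The maintenance conflict does not affect the Group B primary response endpoint, because SAP 6.1.2 takes that response before Cycle 1 Day 1 of maintenance. What is at stake is consistent dosing of neutropenic subjects in remission and consistent coding of deviations and discontinuations. The conclusion rests on reading each rule within its own heading and phase, and takes no view on which clinical rule is right.

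**What to change.** Replace the overlapping Group B text in Protocol 3.3 (the delay text, the non-hematologic removal sentence, the Neutropenia text and the CR/CRi maintenance rule) with one rule set out by phase, cause and agent. It should state:

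- the maximum delay for each cause, and what follows when it is exceeded;
- whether ANC recovery is required before a second or later maintenance cycle, for decitabine and for azacitidine separately;
- whether the repeat marrow is mandatory;
- the phase and toxicity type that the removal sentence covers, with its 4-week limb corrected;
- whether removal from protocol means stopping treatment or leaving the study.

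The sponsor's clinical team chooses the content. The cost is a clarification letter or amendment text, with no change to sample size or analysis method. Important deviations in the NW category of SAP 4.3 should then be coded against the reconciled rule, and the reading applied to subjects treated before it should be recorded in the study report.
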